**Effective**

Version: 2.0

or areas of induration have been noted in the injection area. Nodules are occasionally associated with inflammation or discolouration. The early occurrence of subcutaneous nodules at the injection site (within 3–6 weeks after treatment) may be minimised by adhering to proper dilution and injection techniques. Delayed occurrences of subcutaneous nodules at the injection site (within 1–14 months post injection) have been reported with sometimes a prolonged duration of up to 2 years.

For nodular areas or late granuloma formation, in some cases, they resolved spontaneously or following treatment with multiple intralesional injections of corticosteroids and/or antineoplastic agents (e.g. 5-fluorouracil). Surgical excision of the nodules was sometimes required when they were larger in size, occurring in difficult anatomical regions (e.g. lower eyelid) or persisting after other treatments.

Vascular compromise may occur due to an inadvertent intravascular injection or as a result of vascular compression associated with implantation of any injectable product. This may manifest as blanching, discolouration, necrosis or ulceration at the implant site or in the area supplied by the blood vessels affected; or rarely as ischemic events in other organs due to embolisation. Rare but serious cases of ischemic events associated with temporary or permanent vision impairment, blindness, cerebral ischaemia or stroke have been reported following facial aesthetic treatments.

By April 2018, Sculptra had marketing approval in 18 countries/regions worldwide, including US, EU, Canada, Australia, Hong Kong, Taiwan, South Korea, etc. Sculptra has been proven safe and well tolerated with sustained aesthetic improvement for facial lipoatrophy or volume loss. The primary potential benefit of the study is a perceived improvement in the treated areas. However, there is a risk that the subject will not gain the full aesthetic correction of Midface volume Deficit and/or Midface Contour Deficiency. There is also a risk of device dislocation.

Given the anticipated low level of acceptable adverse events (AE) in connection with the injection, the risk-benefit assessment of the use of Sculptra for treatment of Midface volume Deficit and/or Midface Contour Deficiency appears to offer a clinical benefit at reasonable risk.

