#### 4.7 Schedule of events

**Table 1. Schedule of Events for Group A and Treatment Group**

	Screening	Baseline / Treatment 1	Treatment 2 (Optional) b	Treatment 3 (Optional) b	Treatment 4 (Optional) b	Follow-up	Follow-up	Final visit / Early termination
	D-21 to D1	D1	5W( $\pm 1w$ ) after treatment 1	5W( $\pm 1w$ ) after treatment 2	5W( $\pm 1w$ ) after treatment 3	5W( $\pm 1w$ ) after Last treatment	6M ( $\pm 2w$ ), 9M ( $\pm 2w$ ), 12M ( $\pm 2w$ ), and 18M ( $\pm 3w$ ) after Baseline	24M ( $\pm 4w$ ) after Baseline
Informed consent	X							
Demography	X							
Height		X						
Weight		X					X	X
Medical history & concurrent diseases	X	X a						
Concomitant medication/procedures	X	X a	X	X	X	X	X	X
Vital signs		X c						
Laboratory tests	X						X d	X e
Pregnancy test for childbearing potential women	X	X a,c	X c	X c	X c			X
Inclusion and Exclusion criteria	X	X a						
Randomization		X						

Treatment		X	X	X	X			
MMVS (Blinded Evaluator)	X	X a,c					X	X
MMVS (treating investigator)	X	X a,c	X c	X c	X c	X	X	X
Photography		X c	X c	X c	X c	X	X	X
GAIS (Treating investigator and Subject)			X c	X c	X c	X	X	X
Subject satisfaction questionnaire							X	X
Dispense subject diary		X	X	X	X			
Review and collect subject diary			X	X	X	X		
Device deficiencies		X	X	X	X			
Assessment of AE	X	X a	X	X	X	X	X	X
Study termination								X

- a) Omitted if screening and baseline visit occur on the same day.
- b) The visit is omitted if optional treatment was not performed.
- c) Performed prior to treatment.
- d) Only performed at 12M.
- e) Only performed at early termination if termination occurs before 12M visit.

	
Title 43CHSA1803 Clinical Study Protocol
	
Doc id MA-39381

--	--	-----------------------------------

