1.1 Background

1.1.1 Study design

This is a randomized, multi-center, evaluator-blinded, no-treatment controlled study of Sculptra for correction of Midface Volume Deficit and/or Midface Contour Deficiency in subjects of Chinese origin, men or women aged 18 years or older.

For Group A, after screening, eligible subjects will be treated from day 1 and followed up for 24 months.

For Group B, the study includes two phases as follows:

Main study phase: It is randomized, evaluator-blinded and no-treatment controlled. After screening, all eligible subjects will be randomized either to the Treatment Group or the Control Group in a 2:1 ratio. All the subjects will be followed up for 12 months.

Extension study phase: After the main study phase, the Treatment Group and Group A will be followed up for additional 12 months.

Each Treating Investigator will enroll 1 or 2 subjects as Group A. Before start of enrolment into Group B, the injection technique will be evaluated by the Sponsor or designee of Sponsor and performed after the subjects in Group A for each investigator have received their first treatment and second treatment. If treatments are found to be correctly performed, no further training is needed, there are no outstanding questions regarding the injection technique and no other corrective actions are identified, the enrolment in Group B can start for that investigator.

Each subject assigned to Group A and Treatment Group will receive up to 4 injection sessions with 5 (± 1) weeks intervals. Study treatments should be stopped if optimal midface augmentation has been obtained or a maximum of 4 injection sessions completed. Optimal midface augmentation is defined as the best possible aesthetic result that can be obtained for an individual study participant, as agreed upon by the treating investigator and subject.

Subjects assigned to the Control Group will not receive treatment during the study.

For more details regarding the study, and references, see the Clinical Study Protocol (MA-39381).

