2.2 Analysis Populations

The following populations will be defined:

- Safety
- Includes all subjects in Group B who were treated with Sculptra or randomized to no-treatment group. Subjects are analyzed based on the as treated principle.
- Full Analysis Set (FAS)
- Includes all subjects in Group B who were treated with Sculptra or randomized to no-treatment group. Subjects are analyzed according to the randomisation assignment.
- Per Protocol (PP)
- Includes all subjects in FAS that comply to the protocol procedures with no deviations that can affect the evaluation of the primary variable.

The FAS population is the primary population for all effectiveness analyses. All safety analyses will be based on the Safety population.

For Group A, all analyses will be performed based on all subjects.

 GALDERMA	Title 43CHSA1803 Statistical Analysis Plan - Sculptra China	Doc id MA-40407
--	---	---------------------------

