2.5.3 Adverse events

All AEs will be coded according to MedDRA.

A summary of all AEs, by Treatment Group, will be provided, which will include:

- Number of subjects with at least one AE and number of events (in total as well as serious AEs)
- Number of subjects with at least one related AE and number of events (in total as well as serious AEs)
- Number of subjects with at least one unrelated AE and number of events (in total as well as serious AEs)
- Number of subjects who did not have an AE.

Related AEs as well as number of subjects with related AEs will be summarised by SOC, PT and intensity. In addition, for related AEs the number of days to onset and the duration of event will be summarised by SOC and PT using mean, SD, min, max and median. Action taken for related AEs will also be summarized. Related AEs will be summarized per treatment session.

Serious AEs will be listed.

Late onset (>21 days) AEs will be listed.

Related AEs with late onset (>21 days after most recent treatment) will be listed, if any.

Non-related AEs will be summarised by SOC, PT, and intensity and by Treatment Group.

Time to onset of an AE will be derived as the start date minus the date of most recent treatment. For the Control group date of randomization will be used instead of most recent treatment. If the start date is missing, it will be assumed that the AE started on the day of most recent treatment. If the start month is available but not the day, it will be assumed that the AE started on the first day of the month.

Duration of an AE will be derived as the stop date minus the start date + 1. If the start date is missing, it will be assumed that the AE started on the day of most recent treatment or date of randomization for the Control group. If the start month is available but not the day, it will be assumed that the AE started on the first day of the month. If the stop month is available but not the day, it will be assumed that the AE stopped on the last day of the month. Completely missing stop dates will not be imputed and therefore no duration will be calculated in these cases. Instead, the number of AEs that were ongoing at the end of the study will be given.

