Month 24											

% = (n/N)*100

Note: The main study consists of visits up to 12 months

Table 3-35: Subject Satisfaction Questionnaire, Question 7), Subjects randomized to Sculptra, FAS, OC

Overall, how satisfied are you with the treatment result?									
Visit (after baseline)	Very satisfied		Satisfied		Somewhat satisfied		Not satisfied		Total
	n	%	n	%	n	%	n	%	
Month 6									
Month 9									
Month 12									
Month 18									
Month 24									

% = (n/N)*100

Note: The main study consists of visits up to 12 months

Table 3-36: Subject Satisfaction Questionnaire, Question 8), Subjects randomized to Sculptra, FAS, OC

Did you get any feedback about your look from your family, friends and colleagues?							
Visit (after baseline)	Positive feedback		Negative feedback		No feedback		Total
	n	%	n	%	n	%	
Month 6							
Month 9							
Month 12							
Month 18							
Month 24							

% = (n/N)*100

Note: The main study consists of visits up to 12 months

2019-10-24 08:59

Effective date:

Effective

Version: 1.0

Table 3-37: Subject Satisfaction Questionnaire, Question 9), Subjects randomized to Sculptra, FAS, OC

Visit (after baseline)	Yes		No		Total
	n	%	n	%	
Month 6					
Month 9					
Month 12					
Month 18					
Month 24					

% = (n/N)*100

Note: The main study consists of visits up to 12 months

Table 3-38: Subject Satisfaction Questionnaire, Question 10), Subjects randomized to Sculptra, FAS, OC

Visit (after baseline)	Yes		No		Total
	n	%	n	%	
Month 6					
Month 9					
Month 12					
Month 18					
Month 24					

% = (n/N)*100

Note: The main study consists of visits up to 12 months

2019-10-24 08:59

Effective date:

Effective

Version: 1.0

Treatment procedure**Table 3-39: Volume injected (both cheeks combined), Subjects randomized to Sculptra, Safety population**

Volume injected (mL)						
Visit	N	Mean	SD	Median	Minimum	Maximum
Baseline / Treatment 1						
Treatment 2 (optional)						
Treatment 3 (optional)						
Treatment 4 (optional)						
Total exposure						

Table 3-40: Treatment procedure (both cheeks combined, all treatments combined), Subjects randomized to Sculptra, Safety population

Characteristic	Answer	Statistic	Result
Was 1 ml of lidocaine added to the vial before treatment?	Yes	n (%)	
	No	n (%)	
Local anaesthesia used?	Yes	n (%)	
	No	n (%)	
If local anaesthesia used	Topical cream	n (%)	
	Local infiltration	n (%)	
Needle gauge	25 G	n (%)	
	26 G	n (%)	
Depth of injection	Deep dermis	n (%)	
	Subcutaneous layer	n (%)	

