Serious						
Non-serious						
Unrelated AEs, total						
Serious						
Non-serious						
Subjects with no AE reported						

$$\% = (n/N) * 100$$
Table 3-45: Related Adverse Events by MedDRA SOC and preferred term, Main study, subjects randomized to Sculptra, Safety population

Primary SOC	Preferred Term	Subjects		Events	Maximal Intensity		
		n	%		Mild	Moderate	Severe
Total							

$$\% = (n/number of subjects in the Safety population) * 100$$
Effective

Version: 1.0

	Title 43CHSA1803 Statistical Analysis Plan - Sculptra China	Doc id MA-40407
--	---	---------------------------

**Table 3-46: Related Adverse Events by MedDRA SOC and preferred term, by treatment session,
Main study, subjects randomized to Sculptra, Safety population**

Visit	Primary SOC	Preferred Term	Subjects		Events #	Maximal Intensity		
			n	%		Mild	Moderate	Severe
Baseline / Treatment 1								
Treatment 2 (optional)								
Treatment 3 (optional)								
Treatment 4 (optional)								

% = (n/number of subjects in the Safety population)*100

2019-10-24 08:59

Effective date:

Effective

Version: 1.0

**Table 3-47: Time to onset from last treatment of related AEs,
Main study, subjects randomized to Sculptra, Safety population**

Preferred term	Time to onset (days)					
	n	Mean	SD	Min	Median	Max
Total						

NA = Not Applicable

**Table 3-48: Duration of related AEs,
Main study, subjects randomized to Sculptra, Safety population**

Preferred term	Duration (days)					
	n	Mean	SD	Min	Median	Max
Total						

NA = Not Applicable

**Table 3-49: Action taken of related AEs,
Main study, subjects randomized to Sculptra, Safety population**

Preferred term	Action taken			
	None	Medication treatment	Non-pharmacological treatment or other procedures / tests	Withdrawn
Total				

**Table 3-50: Unrelated Adverse Events by MedDRA SOC and preferred term,
Main study, Subjects randomized to Sculptra, Safety population**

Primary SOC	Preferred Term	Subjects		Events #	Maximal Intensity		
		n	%		Mild	Moderate	Severe
Total							

% = (n/number of subjects in the Safety population)*100

 GALDERMA	Title 43CHSA1803 Statistical Analysis Plan - Sculptra China	Doc id MA-40407
--	---	---------------------------

2019-10-24 08:59

Effective date:

**Table 3-51: Unrelated Adverse Events by MedDRA SOC and preferred term,
Main study, Subjects randomized to no-treatment control, Safety population**

Primary SOC	Preferred Term	Subjects		Events #	Maximal Intensity		
		n	%		Mild	Moderate	Severe
Total							

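### SAP Table 3-46 divides related AEs at the optional later sessions by all Sculptra subjects, so later-session percentages shrink with uptake (minor, descriptive)

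*SAP*

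**What the plan says.** SAP 2.5.3 commits to a by-session display: "Related AEs will be summarized per treatment session". Table 3-46 delivers it, with one row block for Treatment 1 and one for each of the optional Treatments 2, 3 and 4. Its title restricts it to subjects randomized to Sculptra in the Safety population, main study phase. A single footnote serves all four blocks and defines the percentage as "n/number of subjects in the Safety population) * 100". The same footnote wording stands under Tables 3-45, 3-50 and 3-51.

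The later sessions are not given to everyone. SAP 1.1.1 says "Study treatments should be stopped if optimal midface augmentation has been obtained or a maximum of 4 injection sessions completed", and footnote b of Protocol Table 1 adds "The visit is omitted if optional treatment was not performed". Membership of the Safety population does not depend on sessions 2 to 4. SAP 2.2 defines it as: "Includes all subjects in Group B who were treated with Sculptra or randomized to no-treatment group".

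The SAP does not say how an AE is assigned to a session in Table 3-46. The nearest rule, in SAP 2.5.3, concerns timing only: "Time to onset of an AE will be derived as the start date minus the date of most recent treatment". The same section plans a listing of related AEs that start more than 21 days after the most recent treatment.

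The number treated at each session is planned elsewhere, as the N column by visit in Table 3-39 ("Volume injected (both cheeks combined), Subjects randomized to Sculptra, Safety population") and as the performed counts in Table 3-5.

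**The concern.** A subject who was not injected at session 3 cannot contribute an AE to the session 3 rows, yet stays in their denominator. A reader of the session percentages wants to know whether reactions become more or less frequent as injections accumulate. The planned percentage mixes that question with how many subjects went on to another session. When uptake falls, a constant risk per injection prints as a declining risk.

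A second problem lies behind the first. If the onset rule is also used to assign AEs to sessions, a non-final session is observed for about 5 weeks, until the next injection. A subject's last session is observed up to Month 12. This matters for this product, because Protocol 2.6 anticipates late events: "Delayed occurrences of subcutaneous nodules at the injection site", reported 1 to 14 months after injection. The session rows then cover different lengths of follow-up whichever denominator is used.

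At stake is the reading of the only planned table of related AEs by injection session. No test or study decision depends on it.

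**Working it through.** **Inputs from the documents.** Planned Sculptra arm: 126 (SAP 2.7). Session interval: 5 weeks plus or minus 1, taken as 35 days. Main phase: 12 months, taken as 365 days. Table 3-46 is an empty shell, so there is no planned figure to reproduce.

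**Assumptions.** The documents give neither uptake of sessions 2 to 4 nor related-AE rates. All values for these are illustrative. Drop-out is ignored.

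**Step 1: the denominator.** Let n_k be the subjects with a related AE assigned to session k, N_k the subjects injected at session k, and N the Sculptra subjects in the Safety population. Then

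n_k/N = (n_k/N_k) × (N_k/N).

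Example, with all 126 treated, 50 of them injected at a later session and 10 with a related AE: 10/50 = 20.0%, 50/126 = 39.7%, and the table prints 10/126 = 7.9%. Session 1 is correct as planned, because Sculptra subjects enter the Safety population by being treated.

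Range, for uptake of about 80/60/40/20% (101, 76, 50 and 25 of 126):

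| Rate among injected | Printed percentages |
|---|---|
| 10% | 8.0 / 6.0 / 4.0 / 2.0 |
| 30% | 24.0 / 18.1 / 11.9 / 6.0 |

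**Step 2: follow-up per session.** Assume AEs go to the most recent injection and uptake u_k is 1/0.8/0.6/0.4. The share whose last session is k is s_k = u_k − u_(k+1), that is 0.2/0.2/0.2/0.4. Time from session k to Month 12 is L_k = 365 − 35(k − 1), that is 365/330/295/260 days. Mean follow-up per injected subject is [(u_k − s_k) × 35 + s_k × L_k]/u_k:

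- Session 1: (0.8 × 35 + 0.2 × 365)/1 = 101 days
- Session 2: (0.6 × 35 + 0.2 × 330)/0.8 = 109 days
- Session 3: (0.4 × 35 + 0.2 × 295)/0.6 = 122 days
- Session 4: 260 days

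**Step 3: both effects together.** Let p be the chance of an AE straight after each injection and h a constant daily hazard. Then

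n_k (as a share of N) = (u_k − s_k)[1 − (1 − p)e^(−35h)] + s_k[1 − (1 − p)e^(−hL_k)].

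The planned percentage is 100 × n_k. With the injected denominator it is 100 × n_k/u_k. Adding a 21-day onset window gives 100 × [1 − (1 − p)e^(−21h)].

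| Case | Planned footnote | Injected denominator only | Injected denominator and 21-day window |
|---|---|---|---|
| (a) p = 0.15, h = 0 | 15 / 12 / 9 / 6 | 15 at each session | 15 at each session |
| (b) p = 0, h = 0.000408 | 3.9 / 3.4 / 2.8 / 4.0 | 3.9 / 4.2 / 4.7 / 10.1 | 0.9 at each session |
| (c) p = 0.15, h = 0.000408 | 18.3 / 14.9 / 11.4 / 9.4 | 18.3 / 18.6 / 19.0 / 23.6 | 15.7 at each session |

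Case (b), session 4, in full: 0.4 × [1 − e^(−0.000408 × 260)] = 0.4 × 0.1006 = 4.0% planned, and 10.1% of those injected. The windowed value is 1 − e^(−0.000408 × 21) = 0.9%.

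Risk is the same at every session in all three cases. The planned footnote shows a decline in (a) and (c). The injected denominator alone shows a rise in (b) and (c). Only the denominator and the window together give flat rows.

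**The case against.** The strongest defence is that the percentage of all treated subjects is a legitimate quantity and its denominator is disclosed. The counts and event numbers stand beside it, and a reader can rebuild the injected-subject rate from Table 3-39 or Table 3-5. The diary tables already show short-term reactions for each session, and late-onset related AEs are already listed. All of that stands, and it is why the point is minor. It does not make the printed percentages comparable across sessions, which is what a by-session table invites.

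A second objection is that under a constant hazard the planned footnote misleads less than the obvious repair. This is correct, as case (b) shows. The denominator should therefore not be changed without an onset window.

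A third is that the size rests on invented inputs. Also correct: the documents fix the direction of the denominator effect when uptake falls, but not its size. The follow-up argument is conditional too, since the SAP leaves the assignment rule unstated.

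Two stronger readings are tempting. A reader might infer from the Safety definition that untreated controls enter the denominator. The documents do not support this: the table title names the Sculptra subjects, and the same footnote serves other single-arm tables, including the control-only Table 3-51, so it evidently means the arm in the title. A reader might also extend the follow-up imbalance to Month 24 through the combined-phase tables. The SAP repeats tables there only when applicable, so it is not established that Table 3-46 will be among them.

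**Conclusion.** The point holds as a minor defect in a descriptive safety table. The footnote fixes one denominator for four sessions, three of which are optional, and no passage supplies a session-specific one. Each later-session percentage is the rate among injected subjects scaled by uptake: at an assumed 40% uptake, a 15% rate prints as 6%. That step is arithmetic and needs only that an AE assigned to a session occurs in a subject injected at it.

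The follow-up imbalance rests on one further assumption, that AEs are assigned to the most recent injection. With the assumed uptake it is 101 to 122 days for sessions 1 to 3 against 260 days for session 4.

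The finding does not imply that overall AE incidence is understated or that the effectiveness result is in doubt. Counts, event numbers, Tables 3-44 and 3-45 and the primary analysis are not affected.

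**What to change.** - Change the Table 3-46 footnote to: % = (n / number of Sculptra-treated subjects injected at that session) × 100. Print that N on each session row, using the counts already planned for Table 3-39.
- State in SAP 2.5.3 that an AE is assigned to the most recent injection on or before its start date.
- Base the session percentages on related AEs with onset within 21 days of that injection. This is the complement of the SAP's existing late-onset cut. It also fits inside the 4-week minimum interval in Protocol 4.1 and is covered by the visit 5 weeks after the last treatment.
- Show related AEs with onset after 21 days in a separate block, not compared across sessions. This block is needed: Protocol 2.6 places early nodules at 3 to 6 weeks, so many would fall outside the window.

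Cost: one footnote, one N per row, one sentence on assignment, the window and one extra block. No new data are needed. Later-session percentages may look less favourable than under the planned footnote.
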